	Termination visits, and removed	completed at the Early Termination
	PROs (WPAI, PROMIS-29, and	visit only.
	PROMIS-Fatigue 7a) from the	visit only.
	Flare visit.	
	Split the row pertaining to the	Clarification.
	CDAI assessment into 2 rows, one	
	for reminder to complete the	
	electronic CDAI and one for	
	calculation of CDAI.	
	Added footnote for final visit: If	Reducing participant burden of
	clinically appropriate and allowed	frequent site visits, since they will
	by local regulations, the Week 156	have an on-site visit for the Week
	visit can be done by telephone.	152 Final Efficacy Visit.
	Details added for footnote for the	Clarification.
		Clarification.
TTI 1 4 1	Flare visit.	T 1' '4 II 14 A 4 '5
Throughout protocol	Where relevant, changed "clinical	To align with Health Authority feedback.
	recurrence" to "endoscopic" or	feedback.
	"disease recurrence," as	
221D'1-C C(-1-D (' ' ('	appropriate.	Clarification.
2.3.1 Risks for Study Participation,	Added all criteria for cross over to	Clarification.
Risks Table: For risk of clinical	open-label induction and removed mention of clinical recurrence.	
worsening of CD	mention of clinical recurrence.	
4.1 Overall Design, Overall Design	Edited to clarify that the optional	Clarification.
4.1 Overall Design, Overall Design	cross over at Week 24 is at the	Ciarmication.
	discretion of the investigator when	
	there is ONLY endoscopic	
	recurrence.	
4.1 Overall Design, Study Length	Clarified that participation follow-	Clarification.
4.1 Overall Design, Study Length	up may vary for the main study	Clarification.
	period.	
4.3 Justification for Dose	Added all criteria for cross over to	Clarification
ing vastification for Bose	open-label induction and removed	Ciaminoación
	mention of clinical recurrence.	
4.4 End of Study Definition,	Added details for study completion	Clarification.
Participant Study Completion	criteria.	
Definition		
5.1 Inclusion Criteria, #3	Clarified that participants can have	Added to allow for
	undergone an ileocolonic surgical	screening/consent of participants
	resection for CD prior to the	prior to surgery.
	baseline visit.	
5.1 Inclusion Criteria, #13	Edited criterion pertaining to	Clarification.
	adherence to all specified	
	requirements in this protocol to	
	include an ileocolonoscopy at	
	1 year or upon concern for clinical	
	flare.	
6.1 Study Interventions	Details added for dosing upon cross	Clarification and to allow for cross

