ccl site evaluation		х	х	x	х	х	х	х	х	х	х	х	х	х		х	х	Х	An injection site reaction is any adverse reaction at an SC study intervention injection site. Injection sites will be evaluated for reactions and any injection site reaction will be recorded as an AE.

 $CONFIDENTIAL-FOIA\ Exemptions\ Apply\ in\ U.S.$

Study Procedure	Screening Visit (within 5 weeks prior to Week 0)								Stu	dy vis	sits (V	Veek) ^a	1				Flare visit	Early Termination visit ^{a,d}	Notes
		0	8	16	24	32	40	48	64	80	96	112	128	144 Final dose	152 Final efficacy	156 Final safety			
Laboratory Evaluat	ions																		
Hematology and chemistry, CRP	X	х	х	х	х	х	х	х	x	x	х	х	х	x	x	x	x	X	Week 0: laboratory tests are not required if screening laboratory tests were performed within 2 weeks of the Week 0 visit. At Week 156, laboratory tests to be performed only if needed to follow up a prior abnormality.
Blood collection for serum guselkumab concentration and/or anti-drug antibodies ^e		Х	X	х	Х	х		х			х		х		х			х	should be collected before the administration of study intervention. Record the actual times of PK sample collections.
Pharmacodynamics a	and Biomarke	rs (w	here	local	regul	ations	perm	it)											
Serum biomarkers		X			х			х			х				x			х	Serum biomarkers will be collected from all participants to assess peripheral proteins related to both Crohn's disease and response to guselkumab.

Study Procedure	Screening Visit (within 5 weeks prior to Week 0)								Stud	dy vis	sits (V	Week) ^a	ı				Flare visit a,c	Early Termination visit ^{a,d}	Notes
		0	8	16	24	32	40	48	64	80	96	112	128	144 Final dose	152 Final efficacy	156 Final safety			
Whole blood sample collection for RNA analysis		х			х			х			х								Whole blood for RNA analysis will be collected from all participants to assess the RNA transcriptome related to both Crohn's disease and response to guselkumab.
Ileocolonoscopy biopsy sample collections for exploratory RNA and biopsy-based single cell assessments					x			x							х		х		Refer to the biopsy manual for details on the biopsy sample collection. Biopsy sample at Week 24 is obtained only if optional Week 24 ileocolonoscopy is performed.

Study Procedure	Screening Visit (within 5 weeks prior to Week 0)								Stu	dy vis	sits (V	Veek) ^a	1				Flare visit	Early Termination visit ^{a,d}	Notes
		0	8	16	24	32	40	48	64	80	96	112	128	144 Final dose	152 Final efficacy	156 Final safety			
Pharmacogenomics ((DNA))																		

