Genetic (DNA) evaluation (where local regulations permit)		X																	Whole blood will be collected only from participants who consent to participate in the optional DNA analysis. The pharmacogenomic (DNA) sample should be collected at the specified time point; however, if necessary it may be collected later without constituting a protocol deviation.
Efficacy (clinical as	ssessments/C	D-re	lated	healt	hcare	utili	zation	/PRC	Os)										
Electronic daily diary by site staff		x	х	х	х	х	х	x	x	x	x	х	х	х	х		х	х	Remind participant to complete electronic daily diary for the length of the study. The daily diary includes patient-reported data for the CDAI (includes PRO-2 components).

Study Procedure	Screening Visit (within 5 weeks prior to Week 0)								Stu	dy vis	sits (V	Veek)ª	1				Flare visit a,c	Early Termination visit ^{a,d}	Notes
		0	8	16	24	32	40	48	64	80	96	112	128	144 Final dose	152 Final efficacy	156 Final safety			
CDAI assessments		x	x	х	x	x	х	x	x	x	x	X	Х	X	X		X	X	For calculation of CDAI. The hematocrit value obtained during screening will be used to calculate CDAI at Week 0. For all other visits, the hematocrit value from the most recent study visit available will be used to calculate the CDAI.
Weight (component of CDAI)	Х	X	X	х	х	X	x	X	X	x	x	х	Х	х	Х		X	х	In kilograms (kg)
Fistula assessment	X	X	X	X	X	X	X	X	X	X	X	X	X	X	X		X	X	

Study Procedure	Screening Visit (within 5 weeks prior to Week 0)								Stu	dy vis	sits (V	Veek) ^a	ı				Flare visit	Early Termination visit ^{a,d}	Notes
		0	8	16	24	32	40	48	64	80	96	112	128	144 Final dose	152 Final efficacy	156 Final safety			
Video ileocolonoscopy with biopsy and histology					Xf			X^{f}							X f		X	X f	Week 24 procedure is optional, at the discretion of the investigator with agreement of the participant and should be performed ± 14 days from the scheduled visits. Week 48 procedure should be performed between Weeks 48 to Week 51. In the event procedure performed on the day of the designated visit or the 7 days prior, CDAI scores should be calculated using the proximate 7 days that were not impacted by the ileocolonoscopy or its preparation. Refer to the biopsy manual for details on the biopsy sample collection.
Stool sample (fecal calprotectin)	х	х			х		х	х		х			х		х		х		Week 0: Not required if sample already collected during screening is within 2 weeks of the Week 0 visit.

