5. STUDY POPULATION

Screening for eligible participants will be performed within 5 weeks before administration of the study intervention.

The inclusion and exclusion criteria for enrolling participants in this study are described below. If there is a question about these criteria, the investigator must consult with the appropriate sponsor representative and resolve any issues before enrolling a participant in the study. Waivers are not allowed.

The definition of baseline as applied to the inclusion and exclusion criteria below is defined as the Week 0 randomization visit.

The target population is male or female participants (minimum age 18) with a diagnosis of CD who have a qualifying surgery (eg, ileocolonic resection) a maximum of 49 days before randomization. Participants will be excluded if they have a short segment of bowel affected (ie, less than 10 cm) for fibrostenotic disease and they had their first surgery more than 10 years after diagnosis of CD. There is no requirement that participants have failed prior biologics.

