5.1. Inclusion Criteria

Each potential participant must satisfy all of the following criteria to be enrolled in the study:

Age

1. Participants \geq 18 (or the legal age of consent in the jurisdiction in which the study is taking place).

Type of Participant and Disease Characteristic

- 2. Have a documented diagnosis of CD confirmed by endoscopic, histologic, and/or radiologic studies prior to resection or by tissue obtained at resection.
- 3. Have undergone an ileocolonic surgical resection (ie, an intestinal resection with an ileocolonic anastomosis) for CD prior to the baseline visit with the following criteria:
 - Have no known active CD anywhere in the gastrointestinal (GI) tract, including the findings at surgery,
 - Be able to undergo randomization no later than 49 days after surgery, and at least 10 days after surgery (or 8 days after resumption of bowel activity, eg, in case of postoperative ileus),
 - Ileocolonic resection was not for the purpose of removing known dysplasia,
 - If ileocolonic resection occurs > 10 years since the diagnosis of CD and only fibrostenotic stricturing is present, then length of stricture must be > 10 cm

4. Have a baseline CDAI < 200.

Concomitant or previous medical therapies received

- 5. Meets the following requirements for prior or current medications for CD. The following medications are permitted provided that doses meeting the requirements listed below are stable or have been discontinued within the timeframes prior to baseline specified below:
 - Oral corticosteroids at a prednisone-equivalent dose at or below 20 mg/day, or 9 mg/day of budesonide. Participants on corticosteroids should initiate/continue tapering after baseline, per the recommended schedule (see Section 6.8.1.1).
 - Conventional immunomodulators (ie, azathioprine [AZA], 6-mercaptopurine [6-MP], or methotrexate [MTX]) must be discontinued prior to randomization.

Screening Laboratory Tests

- 6. Have screening laboratory test results within the following parameters, and if 1 or more of the laboratory parameters are out of range, a single retest of laboratory values is permitted during the screening period:
 - a. Hemoglobin ≥8.0 g/dL (International System of Units [SI]: ≥80.0 g/L)
 - b. White blood cells $\ge 3.0 \times 10^3 / \mu L$ (SI: $\ge 3.0 \times 10^9 / L$)
 - c. Neutrophils $\geq 1.5 \times 10^3 / \mu L$ (SI: $\geq 1.5 \times 10^9 / L$)
 - d. Platelets $\geq 100 \times 10^3 / \mu L$ (SI: $\geq 100 \times 10^9 / L$)

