The CDAI diary will be completed by participants during the screening period. The investigator or appropriate site personnel will use the hematocrit value obtained during screening to calculate the CDAI score at Week 0.

A minimum of 7 days of CDAI data during the screening period is required to calculate the CDAI score at baseline (Week 0).

Women of childbearing potential must have a negative serum pregnancy test result at screening. Participants must be reminded that they are required to use a highly effective method of contraception during the study (as described in Inclusion Criterion 11) and must continue taking such precautions for 12 weeks after receiving the last administration of study intervention. The method(s) of contraception used by each participant must be documented.

The 'Baseline/Screening' version of the C-SSRS will be conducted during the screening visit and the 'Since Last Visit' version of the C-SSRS will be completed at Week 0.

Participants must undergo testing for TB (Section 8.4.9.1) and their medical history assessment must include specific questions about a history of TB or known occupational or other personal exposure to individuals with active TB. The participant should be asked about past testing for TB, including chest radiograph results and responses to tuberculin skin or other TB testing. A participant's eligibility according to TB screening criteria is described in Section 5.2, Exclusion Criteria.

Week 0 Visit

Prior to entering the study, the participant must be evaluated for eligibility.

An assessment of all previous laboratory results, clinical data, and concomitant medication data will be made by the principal investigator or designee to confirm that the participant satisfies all inclusion criteria and does not violate any exclusion criteria prior to randomization.

Post-baseline Visits

Study visits should occur at the week indicated \pm 10 days. Note that while out of window visits should be recorded as protocol deviations, it is preferable to perform visits and procedures out of window than not perform them at all. One exception may be if sufficient time has passed that it is now in-window for the next subsequent visit, in which case it is advised to contact the medical monitor for assistance in how to best manage the situation.

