4. POPULATIONS (ANALYSIS SETS) FOR ANALYSIS

5. STATISTICAL ANALYSES

5.1. General Considerations

- Unless otherwise specified, for each study, data from all investigational centers/sites will be pooled for analysis
- Study Day 1 refers to the day of the first study intervention administration. All efficacy and safety assessments at all visits will be assigned a day relative to this day.

Study day for a visit is defined as:

- Visit date (date of Study Day 1) +1, if visit date is \geq date of Study Day 1
- Visit date date of Study Day 1, if visit date < date of Study Day 1

There is no 'Study Day 0'.

- Baseline assessment is defined as the last available assessment collected prior to the first study intervention.
- Descriptive statistics (ie, N, mean, median, SD, IQ range, minimum and maximum) will be used to summarize continuous variables. Counts and percentages will be used to summarize categorical variables. Graphical data displays (eg, line plots) may also be used to summarize the data.

CONFIDENTIAL – FOIA Exemptions Apply in U.S.

- The following conventions will be applied for reporting descriptive statistics of all continuous parameters. For presentation, the mean and median will be presented to 1 decimal greater than the original data, SD will be 2 decimal places greater than the original data, and the minimum and maximum will have the same number of decimal places as the original data.
- The following intervention groups will be presented through Week 48, unless otherwise stated:
 - Placebo
 - Guselkumab

Partial dates for adverse events will be imputed as described in Appendix 11.

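### The Week 0 CDAI must use the screening hematocrit, which may pre-date surgery, so eligibility, stratum and the recurrence reference can rest on a pre-operative value

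*Protocol*

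**What the plan says.** Criterion 3 (Protocol 5.1) requires an ileocolonic resection "for CD prior to the baseline visit with the following criteria". The amendment table gives the reason for this wording: to permit "screening/consent of participants" before the operation. Section 5 sets the window: "Screening for eligible participants will be performed within 5 weeks before administration of the study intervention". Criterion 3 allows randomization from 10 to 49 days after surgery.

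The CDAI row of the Schedule of Activities (1.3) reads: "The hematocrit value obtained during screening will be used to calculate CDAI at Week 0". Section 8, Screening Phase, says the same of site staff, who "will use the hematocrit value obtained during screening to calculate the CDAI score at Week 0". Later visits use the most recent hematocrit.

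Two other rows let screening samples replace Week 0 samples. For hematology, chemistry and CRP at Week 0, "laboratory tests are not required if screening laboratory tests were performed within 2 weeks of the Week 0 visit". For fecal calprotectin: "Not required if sample already collected during screening is within 2 weeks of the Week 0 visit". Neither row mentions surgery.

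SAP 5.1 defines baseline differently: "Baseline assessment is defined as the last available assessment collected prior to the first study intervention".

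**The concern.** Screening was opened to the pre-operative period, but the rules for using screening samples as baseline were not adapted. I found no passage that requires these samples to be taken after surgery. The Week 0 CDAI decides eligibility (criterion 4) and the randomization stratum (Protocol 6.3). That stratum returns in the CMH tests, the imputation models and the Cox models of the SAP. The same CDAI is the reference for the 70-point rise in disease recurrence (Protocol 9.4.3), which enters the first two secondary endpoints. If its hematocrit is pre-operative and that of later visits is post-operative, part of the change from baseline is only a change of sample.

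The rule also discards better data. When screening labs are more than 2 weeks old, Week 0 hematology is drawn, but the text still directs the older hematocrit into the CDAI. The same participant can then have one baseline hematocrit in the hematology tables and another inside the baseline CDAI.

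**Working it through.** The plan gives no figure to reproduce here. The check is date arithmetic and the CDAI formula.

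Inputs:
- screening up to 35 days before Week 0 (Protocol Section 5);
- surgery 10 to 49 days before randomization (criterion 3);
- substitution window of 14 days (1.3);
- hematocrit term 6 × (47 − Hct) for men and 6 × (42 − Hct) for women (SAP 6.12.3);
- CDAI limb of disease recurrence: a rise of at least 70 and a CDAI of at least 200, with endoscopic recurrence (Protocol 9.4.3);
- assumption: the screening and Week 0 hematocrit differ by 4 to 8 points. The documents give no perioperative change in size or direction.

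Timing of the hematocrit. The screening value can be pre-operative when surgery was fewer than 35 days before Week 0. That is randomization on days 10 to 34, or 25 of the 40 permitted days. The longest lead is 35 − 10 = 25 days before surgery.

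Timing of substituted labs, CRP and stool. These can be pre-operative only when surgery was fewer than 14 days before Week 0, so days 10 to 13, by at most 14 − 10 = 4 days. From day 14 the 2-week limit forces a post-operative sample.

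Shift in CDAI: 4 × 6 = 24 and 8 × 6 = 48 points.

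Eligibility and stratum. If the screening hematocrit is the higher one, baseline CDAI is understated:
- a true value of up to just under 200 + 24 = 224 (or 248) reads as below 200;
- a true value of up to just under 150 + 24 = 174 (or 198) reads as below 150;
- a true 210 is recorded as 186 (or 162).

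If the screening hematocrit is the lower one, baseline is overstated: a true value from 200 − 24 = 176 (or 152) reads as ineligible, and from 150 − 24 = 126 (or 102) it reads as 150 or more.

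Recurrence trigger. The CDAI needed is max(200, baseline + 70), so the floor of 200 governs up to a baseline of 130.

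| True baseline | Recorded | True trigger | Recorded trigger | Change |
|---|---|---|---|---|
| 130 | 82 (−48) | 200 | 200 | 0 |
| 150 | 102 (−48) | 220 | 200 | −20 |
| 154 | 130 (−24) | 224 | 200 | −24 |
| 178 | 130 (−48) | 248 | 200 | −48 |
| 100 | 148 (+48) | 200 | 218 | +18 |
| 130 | 154 (+24) | 200 | 224 | +24 |

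The trigger moves only if the true or the recorded baseline exceeds 130. For an understated baseline, the full shift needs a true baseline of at least 130 + 24 = 154 or 130 + 48 = 178.

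Only the hematocrit term is exposed. Weight is measured at Week 0, and SAP 6.12.2 takes diary data from the 7 days before the visit, which are post-operative when surgery was at least 10 days earlier.

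**The case against.** The text permits a pre-operative hematocrit but does not force one: screening can continue past surgery, and a value obtained during it may be post-operative. Eligibility is reconfirmed at Week 0, and the note closing Section 5.2 excludes anyone whose status changes on available results. A Week 0 blood result may also not be back from the central laboratory when the CDAI is needed for randomization. These points stand, but they do not close the gap. None of the safeguards requires a new sample, and the practical reason supports a recent screening value, not a pre-surgical one. SAP 5.1 could be read as referring to the assembled CDAI score, which removes the formal conflict but leaves the older component inside the score.

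Four stronger readings are tempting and not supported:
- The primary result is biased. The primary endpoint is a centrally read Rutgeerts score plus intercurrent events. Baseline CDAI could reach it only indirectly, through the flare-visit endoscopy threshold and cross over. The hematocrit error is fixed before randomization and unrelated to arm, so a wrong stratum costs some precision and does not bias the comparison.
- The 70-point criterion is distorted by 24/70 = 34% to 48/70 = 69% in general. The floor of 200 removes or reduces the effect for many baselines, and the steroid, fistula and abscess limbs do not use baseline CDAI.
- Change in CRP and calprotectin mostly measures the operation, or calprotectin recurrence becomes unattainable. This could arise only for randomization on days 10 to 13, with a high pre-operative value, and these endpoints are exploratory.
- Dosing generally proceeds with no post-operative blood. From day 14 a Week 0 sample is drawn before dosing. What is missing is a requirement that its result be seen first.

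**Conclusion.** The point holds for the hematocrit rule and, more narrowly, for the substituted samples. The Week 0 CDAI rule can put a pre-operative hematocrit into the baseline on 25 of the 40 permitted randomization days, and it overrides a newer Week 0 value where one exists. The second defect needs no assumption about surgery and also touches participants screened after it. The size, 24 to 48 CDAI points, rests on the assumed 4-to-8-point difference, and its direction is unknown. Eligibility and stratum are exposed near their cut-offs, and the recurrence trigger only as tabulated. Criterion 6 is judged on screening labs that may be pre-operative.

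The practical effect is small. SAP Section 1 reports that the study was discontinued with four participants enrolled and that the planned analyses no longer apply. The point therefore concerns the plan as written, any reuse of it, and the CDAI, CRP and calprotectin values still to be reported for those four.

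**What to change.** - In Protocol 1.3 and Section 8, state that the hematocrit for the Week 0 CDAI is the most recent value from a sample taken after surgery.
- In 1.3, state that the 2-week waiver for hematology, chemistry, CRP and stool applies only to post-surgery samples.
- In the SAP, compute baseline CDAI with the Week 0 hematocrit where one was drawn, in line with SAP 5.1, and say whether stratified analyses use the stratum as randomized or as recomputed.
- Reconcile criterion 6 with the changed-status note at the end of Section 5.2 for participants screened before surgery.
- For the four enrolled participants, note in the report whether each baseline sample preceded surgery.

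The cost is a few sentences and, for some participants, a short wait for a blood result before randomization. Week 0 blood and stool are already scheduled, and recomputing baseline CDAI needs no new data.

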2. INTRODUCTION

Guselkumab is a fully human immunoglobulin G1 lambda (IgG1 lambda) monoclonal antibody (mAb) that binds to the p19 subunit of human interleukin (IL)-23 with high specificity and affinity. The binding of guselkumab to the IL-23p19 subunit blocks the binding of extracellular IL-23 to the cell surface IL-23 receptor, thus inhibiting IL-23 specific intracellular signaling and downstream activation and cytokine production. In this manner, guselkumab inhibits the biological activity of IL-23 in all in vitro assays examined.

Guselkumab (CNTO1959, TREMFYA®) is currently approved for the treatment of adults with moderate-to-severe plaque psoriasis (in patients who are candidates for systemic therapy or phototherapy) and moderate-to-severe psoriatic arthritis, in the United States (US), European Union (EU), Canada, and several countries in Latin America and the Asia-Pacific region. Guselkumab has also been approved for the treatment of generalized pustular psoriasis, erythrodermic psoriasis, and palmoplantar pustulosis in Japan. In addition, guselkumab is being evaluated in both moderate to severe ulcerative colitis (UC) and Crohn's disease (CD), as well as in several other immune-mediated dermatologic and rheumatologic diseases globally.

For the most comprehensive nonclinical and clinical information regarding guselkumab, refer to the latest version of the Investigator's Brochure (IB) and Addenda for guselkumab.

The term "study intervention" throughout the protocol, refers to study drug as defined in Section 6.1, Study Interventions Administered.

The term "sponsor" used throughout this document refers to the entities listed in the Contact Information page(s), which will be provided as a separate document.

